6. SAFETY ANALYSES

All analyses of safety including the extent of exposure to study medication will be performed using the Safety population.

No statistical testing will be performed for comparisons of safety endpoints.

6.1. Study Medication Exposure and Treatment Compliance

Extent of Exposure

Time on study will be derived for each patient as:

- Time on study = Date of last visit – Date of randomization + 1.

The extent of exposure to study drug will be derived for each patient as:

- Extent of exposure = Date of last dose of study drug – Date of 1st dose of study drug + 1.

Time on study and extent of exposure will be descriptively summarized for each treatment sequence and treatment arm.

Treatment Compliance

Patient compliance with study drug will be assessed at each visit. Compliance will be assessed by counting returned tablets. The patient will be considered significantly noncompliant if he or she takes < 80% or > 120% of the dispensed tablets. Deviations from the prescribed dosage regimen should be recorded.

Treatment compliance will be calculated for each treatment phase using the formula:

- Treatment Compliance = $100 \times (\text{number of capsules received}) / (\text{number of capsules intended})$.

The total number of tablets intended is equal to the number of days the patient spent in the treatment phase.

Treatment compliance will be descriptively summarized for each treatment arm.

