7.2. Method of Treatment Assignment

Patients who meet all criteria for enrollment will be randomized in 1:1:1 to 1 of 3 treatment arms: PRCL-02 Dose 1, PRCL-02 Dose 2, or placebo. Assignment to treatment groups will be determined by a computer-generated random sequence using an interactive web-response system (IWRS). The IWRS will be used to assign blister packs containing double-blind drug product to each patient. The IWRS system will be programmed to balance the treatment arms according to

weight (<95kg and \geq 95kg), and prior number of failed therapies (<3 and \geq 3). The purpose of the algorithm is to maintain approximately the same proportion of patients for these variables in each treatment arm.

During the patient's dispensing visits, the site will access the IWRS for the correct blister pack number to dispense. The drug product will be dispensed in a kit, which will provide amounts of treatment consistent with the dispensing plan (Section 7.1) and the allowed window period (Table PRCL 1). The patients will be provided with sufficient treatment to last until the next dispensing visit. (Table PRCL 1).

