7.6. Treatment Compliance

Patient compliance with study drug will be assessed at each visit. Compliance will be assessed by counting returned tablets. The patient will be considered significantly noncompliant if he or she takes <80% or >120% of dispensed tablets. Deviations from the prescribed dosage regimen should be recorded in the electronic data capture (EDC).

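### SAP 6.1 leaves the extra Day 1 loading tablets out of the compliance denominator, and the 80%/120% flag uses a different denominator under which the upper limit cannot be exceeded (minor)

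*SAP*

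**What the plan says.** SAP 6.1 gives a compliance percentage and a noncompliance flag.

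- **Percentage.** The numerator is the "number of capsules received" and the denominator is the number intended, which the SAP defines as follows: "The total number of tablets intended is equal to the number of days the patient spent in the treatment phase". The percentage is to be calculated for each treatment phase and summarised by arm. The phase is not defined.
- **Flag.** "The patient will be considered significantly noncompliant if he or she takes < 80% or > 120% of the dispensed tablets". Protocol 7.6 has the same rule. Both documents say that compliance is assessed by counting returned tablets, and at every visit. Neither gives the period over which the flag is computed.

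The proportion of patients flagged is a planned by-arm summary in the Safety population (Protocol 10.3.2.4).

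The regimens are in Protocol 7.1 and SAP 2.4. Dose 1 is 150 mg on Day 1, then 25 mg daily from Day 2. Dose 2 is 300 mg on Day 1, then 50 mg daily from Day 2. The Protocol synopsis says that all arms have a loading dose, and Protocol 7.1 gives tablet strengths of 25 mg and 50 mg. The last dosing day is Day 85 (Protocol Section 2, footnote k; SAP Section 7).

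**The concern.** The loading dose is six times the maintenance dose, and no listed strength delivers it in one tablet. A denominator of one tablet per day therefore does not describe the regimen, and perfect adherence does not score 100%.

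The flag has a different fault. It compares tablets taken with tablets dispensed. That ratio has a ceiling of 100%, and it counts as not taken any tablets that were handed out but never fell due because treatment had stopped. Nothing in either document connects the flag to the percentage, so the same section carries two denominators and neither is tablets scheduled.

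At stake is whether the two compliance summaries can be read at face value. The numerator is also loosely worded: the product is a tablet, and received could mean dispensed or taken. The terms treatment phase and treatment sequence do not fit a single-period parallel design.

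**Working it through.** The documents give no tablet total or compliance result, so there is no stated figure to reproduce.

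**Inputs.** Let L be the number of Day 1 loading tablets and m the number of maintenance tablets per day. Days 2 to 85 are 84 maintenance days. L and m are not stated and are assumed here:

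- Main case: L = 6 (150/25 or 300/50), m = 1.
- Low case, Dose 1 only: L = 3 (150/50), m = 1.
- High case, Dose 2 from 25 mg tablets only: L = 300/25 = 12, m = 50/25 = 2.

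In every case L is more than 1.

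**1. Percentage, completer.** Tablets scheduled = L + 84m. SAP tablets intended = 85.

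| Case | Scheduled | Adherent score under SAP 6.1 |
|---|---|---|
| L = 6, m = 1 | 6 + 84 = 90 | 90/85 = 105.9% |
| L = 3, m = 1 | 3 + 84 = 87 | 87/85 = 102.4% |
| L = 12, m = 2 | 12 + 168 = 180 | 180/85 = 212% |

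In the main case a completer who misses 5 maintenance doses takes 85 tablets and scores 85/85 = 100%. With L = 3, 2 missed doses have the same result.

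**2. Percentage, early stopper.** Main case, last dose on Day 7: tablets taken = 6 + 6 = 12.

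- If the treatment phase ends that day: 12/7 = 171%.
- If it ends at a visit on Day 14: 12/14 = 86%.

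The error can go either way, depending on a term that the SAP does not define.

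**3. Flag, upper limit.** Taken = dispensed − returned, so taken/dispensed = 1 − returned/dispensed, which is at most 100%. A value above 120% is impossible.

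**4. Flag, lower limit.** Dispensing is on Days 1, 8, 15, 29 and 57. In the main case with no spare tablets, 90 have been dispensed in total once the Day 57 kit is handed out. An adherent patient whose last dose is on Day 57 has taken 6 + 56 = 62, so the ratio is 62/90 = 68.9%, below 80%. Taking the Day 57 dose from the old or the new kit does not change this cumulative figure. Spare tablets would lower it.

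**5. Flag, adherent completer, cumulative.** With no spares, 90/90 = 100%. With 2 spares in each of the five kits (an illustration based on the ±2-day visit window), 90/100 = 90%. Neither is flagged.

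**The case against.** The strongest reply is that little depends on this. Compliance defines no population and enters no test. An adherent completer scores 105.9% in the main case and is not flagged on a cumulative count of dispensed tablets. Early stopping and misuse also appear elsewhere in the plan: "Time on study and extent of exposure will be descriptively summarized for each treatment sequence and treatment arm", and "Deviations from the prescribed dosage regimen should be recorded". SAP 4.2 also tabulates protocol violations by arm. All of this stands, and it is why the point is minor.

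The tablet counts can also be challenged. The low case would give Dose 1 fewer Day 1 tablets than Dose 2 in a double-blind trial unless placebo tablets made up the number. That affects the size of the error; its existence needs only more than one tablet on Day 1.

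A reader might infer more than the documents support:

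- **That adherent early stoppers always score too high.** This requires the treatment phase to end on the day of the last dose. SAP 6.1 uses that date for extent of exposure but does not say so for compliance, and Protocol Section 2 (footnote b) provides a visit after early discontinuation.
- **That the number of stop days or patients wrongly flagged can be counted.** Protocol 7.2 says that kits allow for the visit window but gives no kit size, and the timing of discontinuations is unknown.
- **That the comparison between arms is biased.** Loading applies to every arm. A difference could arise if stopping times differed between arms, but nothing in the documents shows that they would.

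**Conclusion.** Wrong as written, with minor impact. Two statements hold without any assumption about supply beyond the listed strengths: the intended count omits loading tablets, and the limit above 120% cannot be met against tablets dispensed.

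The sizes rest on assumptions. With 6 loading tablets, one maintenance tablet per day and a last dose on Day 85, an adherent completer scores 105.9%; with 3 loading tablets, 102.4%. With Dose 2 supplied only as 25 mg tablets, the score is 212%. For early stoppers, neither the size nor the direction of the error can be fixed until the treatment phase is defined. The 68.9% example assumes no spare tablets and a cumulative count.

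The consequence is confined to the by-arm compliance percentage and the by-arm proportion significantly noncompliant.

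**What to change.** Use one ratio in SAP 6.1 and Protocol 7.6:

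100 × tablets taken (dispensed minus returned) / tablets scheduled under the assigned regimen, from first dose to the end of treatment or the documented treatment discontinuation.

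Count loading and maintenance tablets at the strength supplied. Replace the capsule wording in the numerator with tablets taken. Apply the existing 80% and 120% limits to this ratio over the whole treatment period.

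In the main case an adherent patient then scores 100% on any stop day (Day 57: 62/62), and a completer who misses 5 doses scores 85/90 = 94.4%. For a completer the limits correspond to fewer than 72 or more than 108 tablets.

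The upper limit will still rarely be reachable for completers, because taken cannot exceed dispensed. More than 18 spare tablets would be needed (108 − 90); with 2 spares per kit the maximum is 100/90 = 111%.

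The cost is one revised derivation and matching wording in the protocol, with no change to dosing. Tablet accountability is already scheduled, including at early termination. Compliance will remain uncertain for patients who do not return their kits.

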6.2. Adverse Events

Summaries of AEs will include the number of patients with at least one AE for each treatment group. When reporting by system organ class (SOC) and preferred term (PT), the reports will present the SOC in alphabetical order; while PTs within the SOC will be presented in order of overall decreasing frequency of occurrence overall. A patient with multiple AEs (different PTs) coded to the same SOC will be counted only once for that SOC, but will be counted each time for different PTs within that SOC. A patient with separate events of the same PT (different start/stop dates) will be counted only once in the frequency tables for that PT.

Summaries of AEs will include the number of patients with at least one AE for each treatment group. When reporting by system organ class (SOC) and preferred term (PT), the reports will present the SOC in alphabetical order; while PTs within the SOC will be presented in order of overall decreasing frequency of occurrence overall. A patient with multiple AEs (different PTs) coded to the same SOC will be counted only once for that SOC, but will be counted each time for different PTs within that SOC. A patient with separate events of the same PT (different start/stop dates) will be counted only once in the frequency tables for that PT.

Treatment-Emergent Adverse Events

Treatment-emergent adverse events (TEAE) include all adverse events that emerge or worsen after taking the first dose of study drug. TEAEs will be summarized for each treatment group by SOC and PT, and by PT in order of decreasing frequency of preferred term.

Serious Adverse Events

Treatment-Emergent SAEs will be summarized for each treatment arm by SOC and PT. These reports will also include the total number of SAE for each SOC and PT.

Treatment-Emergent Adverse Events Resulting in Death

If there are any TEAEs that result in death, a listing of all deaths will be provided. In addition, a summary table may also be created by PT in order of decreasing frequency of preferred term.

Treatment-Emergent Adverse Events Leading to Study Drug Discontinuation

TEAEs for which the action taken with medication is 'Drug Withdrawal' will be identified as TEAEs that lead to study drug discontinuation. The TEAEs that lead to study drug discontinuation will be summarized for each treatment group by SOC and PT for the Safety population. A by-patient listing of the TEAEs that lead to study drug discontinuation will also be provided.

Treatment-Related Treatment-Emergent Adverse Events

Every AE will be assessed by the investigator for its relationship to the randomly assigned study medication. The subset of TEAEs considered by the investigator as either possibly, probably, or definitely related to study treatment will be summarized as drug-related TEAEs by SOC and PT.

Treatment-Emergent Adverse Events by Maximal Severity

Every AE will be graded by the investigator as mild, moderate, or severe, so for each patient the greatest severity observed can be obtained by comparing the severity of all of a patient's TEAEs that share the same SOC or PT. A table of TEAEs by maximal severity will be prepared for each treatment arm by SOC and PT.

Treatment-Emergent (Not Including Serious) Adverse Events

The most common non-serious TEAEs will be summarized. All PT that occur in at least 5% of the Safety Population patients in any treatment group, when not counting the serious TEAEs, will be tabulated by SOC and PT for each treatment group. These reports will also present the total number of TEAEs for each SOC and PT.

6.3. Clinical Laboratory Analyses

Blood samples for hematology and clinical chemistry and urine samples for urinalysis will be collected. Profiles for the hematology, clinical chemistry and the numeric urinalysis parameters will be summarized, and extreme values for select parameters during the on-treatment period during the study will be summarized.

6.3.1. Clinical laboratory assessments over time

Change from baseline for each of the hematology, clinical chemistry and the numeric urinalysis parameters will be derived for each of the post-dose time points using the pre-dose measurement as the baseline. Descriptive statistics for the measurement at baseline and the measurement and change from baseline at each post-dose time point will be tabulated.

6.3.2. Clinical laboratory shift tables

Each laboratory parameter will be classified as low, normal or high relative to the central laboratory's normal range. For each treatment group shift tables will be generated from the pre-dose category to the category post-dose for each laboratory parameter. The shift tables will present the number (percent) of patients who started in a category (low, normal, high) at baseline and ended in a category at the end of the study. A missing category will be included for both pre-dose and post-dose, so that all patients in the Safety population will be represented in the table. The percentages will be calculated using number of patients in the Safety population who have measurements at pre-dose and post-dose.

Shift tables comparing pre-dose to the other time points in the study may be generated if warranted after data review.

Similar shift tables for the categorical urinalysis parameter will also be produced using all categories reported for a parameter during the study.

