5.1. Overall Design

This is a multicenter, randomized, double-blind, placebo-controlled, parallel design Phase 2a study in patients with moderate to severe chronic plaque psoriasis.

Screening (up to 28 days prior to first dose of study drug) allows for evaluation of inclusion and exclusion criteria. Following Screening, all eligible patients will be randomly assigned (in 1:1:1 ratio) to PRCL-02 Dose 1, PRCL-02 Dose 2, or placebo and will receive study drug for 12 weeks. Following completion of 12-week treatment, all patients will attend Follow-Up Visits at 2, 4, 6 and 8 weeks after the last dose of study drug.

Efficacy and safety assessments will be performed as defined in the Schedule of Activities (Section 2).

Figure PRCL 1 illustrates the study design.

Study governance considerations are described in detail in [Appendix 3](#).

[figure not shown]

Figure PRCL 1

Illustration of study design for Clinical Protocol PRCL-PoC

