7. PHARMACOKINETIC/PHARMACODYNAMIC ANALYSES

Pre-dose samples are to be obtained at 1 week, 2 weeks, 4 weeks and 8 weeks after the first dose of study drug. On the last day of dosing (Day 85/Week 12), the following samples are to be collected: pre-dose and 1, 2, 4, 8, 24 (Day 86), 72 hr (Day 88), and 168 hr (1 week; Day 92) post dose. One sample should be taken at the EOS visit (at least 6 weeks after the last dose [Week 18]). One sample should be taken at the early termination visit, if applicable.

Pharmacokinetic parameters will be summarized by dose level using descriptive statistics. PK parameters such as the maximum concentration (C_{max,ss}), time of maximum concentration (T_{max,ss}), area under the concentration versus time curve within a dosing interval (AUC_{0- τ ,ss}), the first-order terminal elimination rate constant (λ_z), the terminal elimination half-life (t_{1/2}), apparent clearance (CL/F), and apparent volume of distribution (V_d/F) will be reported. Other parameters may be calculated as deemed appropriate. Mean and individual PRCL-02 plasma concentration-time curves will be represented graphically.

Note that for all PK parameters but T_{max}, summary statistics will include geometric mean and geometric CV%. T_{max} will be reported as median and range (minimum to maximum).

The PK/PD relationship of PRCL-02 with PD, efficacy, and/or safety measures may be explored.

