9. SCHEDULE OF ASSESSMENTS

Procedure	Screening									FU	EoS
Visit #	1	2	3	4	5	6	7	8	9	10	11
Study Days	-28 to -1	1	8	15	29	57	85	99	113	127	141
Window Period (Days)		±2	±2	±2	±2	±2	±2	±2	±2	±2	±2
Week	-	-	1	2	4	8	12	14	16	18	20
Informed consent	X										
Demographics	X										
Medical history	X										
Inclusion and exclusion criteria	X	X									
Pregnancy test (♀)	X	X	X	X	X	X	X	X	X	X	
Serum FSH (PMP ♀)	X										
QuantiFERON TB Test		X									
HIV/hepatitis screen	X										
Randomization		X									
Study drug dispensing		X	X	X	X	X					
Study drug accountability			X	X	X	X	X				X if ET
Safety Evaluations											
Physical examination	X	X	X	X	X	X	X				X
Height/weight	X	X	X	X	X	X	X				X
Vital signs (pulse and BP)	X	X	X	X	X	X	X	X	X	X	X
12-lead ECG	X	X	X	X	X	X	X				X
Clinical laboratory tests	X	X	X	X	X	X	X				X
AE monitoring	X	X	X	X	X	X	X	X	X	X	X
Concomitant medications	X	X	X	X	X	X	X	X	X	X	X
Efficacy and Other Evaluations											
PASI	X	X	X	X	X	X	X	X	X	X	X
sPGA	X	X	X	X	X	X	X	X	X	X	X
PK sampling			X	X	X	X	X	X	X	X	X
Plasma sample collection for PGx assessments		X									

See protocol for footnotes.

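### The only laboratory shift table the SAP commits to runs from baseline to end of study, which for completers is 56 days after the last dose; no committed output counts category changes on treatment.

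*SAP*

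**What the plan says.** SAP 6.3.2 opens in general terms: "shift tables will be generated from the pre-dose category to the category post-dose for each laboratory parameter". Its next sentence makes this specific: the tables give the number and percentage of "patients who started in a category (low, normal, high) at baseline and ended in a category at the end of the study". Anything else is discretionary: "Shift tables comparing pre-dose to the other time points in the study may be generated if warranted after data review". The urinalysis tables follow the same pattern and add no time point: "Similar shift tables for the categorical urinalysis parameter will also be produced using all categories reported for a parameter during the study".

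SAP section 7 places the end of dosing: "On the last day of dosing (Day 85/Week 12), the following samples are to be collected". Protocol 5.1 says that "all patients will attend Follow-Up Visits at 2, 4, 6 and 8 weeks after the last dose of study drug". In both schedules (Protocol Table PRCL 1 and SAP section 9) laboratory tests are marked at screening, on Days 1, 8, 15, 29, 57 and 85, and then only in the EoS column, Day 141. Footnote b of the protocol table has patients who discontinue early undergo the EoS activities.

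The documents commit to three other laboratory outputs:
- SAP 6.3.1: descriptive statistics for value and change from baseline at every post-dose time point. Under SAP section 8 these generally include minimum and maximum.
- SAP 6.3: a summary of on-treatment extreme values for selected parameters, with neither the parameters nor the limits named.
- Protocol 10.3.4: laboratory parameters are listed as well as summarized.

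**The concern.** Safety and tolerability over 12 weeks of dosing is a secondary objective. SAP section 6 plans no safety testing, so descriptive tables carry the evidence. A shift table shows how many individual patients moved out of the normal range. If its second axis is a value taken 8 weeks after dosing stopped, a patient who was normal at baseline, high at Weeks 4 to 12 and normal at Week 20 is counted as normal to normal. The protocol itself treats on-treatment liver tests and blood counts as grounds for considering or requiring discontinuation (Protocol 8.1), so these are changes the report should be able to count.

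The column is also not homogeneous. An early terminator's value is taken around withdrawal and a completer's 8 weeks after the last dose. Arms with different withdrawal rates could therefore differ partly through timing.

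**Working it through.** **Inputs.** Last dose Day 85 (SAP section 7). EoS Day 141, visit windows ±2 days, laboratory visits as listed above (SAP section 9; Protocol Table PRCL 1). Arm size 27 and drop-out 10% (SAP 1.3).

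**1. Reproduce the plan's own interval.** Maintenance dosing starts on Day 2 and runs 12 weeks (84 days): 2 + 84 − 1 = Day 85, which agrees with SAP section 7. Follow-up visits on Days 99, 113, 127 and 141 fall 14, 28, 42 and 56 days after Day 85, which are the 2, 4, 6 and 8 weeks of Protocol 5.1.

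**2. Gap for a completer.** 141 − 85 = 56 days. With windows, the shortest is (141 − 2) − (85 + 2) = 52 and the longest (141 + 2) − (85 − 2) = 60. SAP section 7 puts the EOS visit at Week 18; on that timing the gap is 127 − 85 = 42 days. The two SAP passages need reconciling, but both put the value well after the last dose.

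**3. Does another reading of the end of the study help?** SAP 6.3.2 does not define it. Read as the EoS visit, it is Day 141. Read as the last available post-dose value, it is still Day 141 for a completer, because that is the last scheduled laboratory visit. Only end of treatment would close the gap, and 6.3.2 does not say that.

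**4. Visits used.** Five scheduled laboratory visits fall in the dosing period after baseline (Days 8, 15, 29, 57 and 85). For a completer the committed table uses none of them.

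**5. Patients affected.** 27 × (1 − 0.10) = 24.3, so about 24 per active arm. The remaining 2.7 or so contribute an early-termination value.

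**6. Bounding case for the mixing.** Suppose a fraction q of an active arm is abnormal at the last on-treatment value, every such change has reversed by Day 141, a fraction d withdraws early with values taken on drug, and q is the same in both groups. The table then shows d × q instead of q. At d = 10% that is one tenth of the true on-treatment frequency. Two active arms with equal q but drop-out d1 and d2 would differ by q × (d1 − d2) from timing alone. This is the extreme; partial reversal gives less.

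**7. How much drug is left at 56 days?** The documents give no half-life, so this is an assumed range using 0.5^(56/h), with h the half-life in days. The first row assumes that the 6:1 loading-to-maintenance ratio equals the accumulation ratio: k = −ln(1 − 1/6), h = ln 2 / k = 3.8 days.

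| Assumed half-life (days) | Drug remaining at 56 days |
|---|---|
| 3.8 | below 0.01% |
| 7 | 0.4% |
| 14 | 6% |
| 28 | 25% |

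The value is therefore post-treatment under every assumption. Whether it is drug-free depends on a figure the documents do not give.

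**The case against.** The strongest reply is that on-treatment laboratory data are not missing from the report. The by-visit summaries cover every on-treatment visit, and a markedly high liver value would appear as that visit's maximum. On-treatment extremes are promised, individual values are listed, and Protocol 9.4.3 and 9.4.5.1 provide for adverse event reporting, repeat liver testing and extra hepatic data. No safety comparison is tested, so no inference is biased. SAP 6.3.2 anticipates more shift tables, and SAP 1.1 lets supportive analyses be added without amendment.

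Most of this stands, and it limits the point to categorical shifts. It does not remove it. A maximum shows one patient, not how many crossed a limit. The extremes summary names no parameter and no threshold, whereas vital signs (SAP 6.4) and QTc (SAP 6.5) have explicit limits and patient counts. Protocol 9.4.3 asks for a laboratory finding to be reported as an adverse event when it is clinically significant and results in a diagnosis, so a reversible shift without a diagnosis need not appear there. An option exercised after data review is not a pre-specified output.

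A reader might infer three stronger claims that the documents do not support:
- That a transient abnormality would be invisible in the safety report. It could be hidden in this table only.
- That an arm with more withdrawals would look worse purely because of timing. Footnote b does not say how soon after the last dose the early-termination visit falls, and an abnormal on-drug value may be a real drug effect.
- That about 24 of 27 patients in every arm give an off-drug value. Placebo patients are never on drug, so the contrast applies to the two active arms.

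**Conclusion.** The point holds in a limited form. The one committed shift comparison uses, for completers, a value 56 days after the last dose (52 to 60 with windows; 42 on the Week 18 timing), and no committed output counts patients who changed category on treatment. About 24 of 27 patients in each active arm are affected, if the planned 10% drop-out holds and all drop-outs leave before EoS. Loss of a reversible shift is possible, not certain: it depends on how quickly an abnormality resolves and on a half-life the documents do not give. The mixing of early-termination and Day 141 values could contribute to differences between arms; its size cannot be fixed from the documents. The primary efficacy analysis is untouched. The change is worth making before database lock because the better table is cheap and the present one does not describe the dosing period.

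**What to change.** In SAP 6.3.2, replace the single comparison with committed tables by treatment group:

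- (a) Baseline category to category at the last on-treatment value.
- (b) Baseline category to worst on-treatment category, low and high separately, including unscheduled values. SAP 2.6 otherwise carries findings from unscheduled visits only into adverse event and disposition summaries.
- Define on-treatment by a stated number of days after the last dose, so that an early-termination value is classified by rule.
- Keep baseline to Week 20 as a separate table labelled post-treatment follow-up, and state how early-termination values enter it.
- Reconcile the Week 18 EOS timing in SAP section 7 with Week 20 in the schedule.

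The cost is SAP wording, which may need an amendment under SAP 1.1 if the plan is already approved, and two more tables. The samples and data are already in the schedule.
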